#### **8.5.1.4. Treatment of Outliers in Pharmacokinetic Analysis**

If a value is considered to be anomalous due to being inconsistent with the expected PK profile, it may be appropriate to exclude the value from the PK analysis. However, the exclusion of any data must have strong justification and will be flagged in data listings and documented in the CSR.

Any quantifiable predose concentration value will be considered anomalous and set to missing for the PK analysis. This will be set to 0 by default in Phoenix WinNonlin.

#### **8.5.2. Presentation of Pharmacokinetic Data**

If the actual time of sample collection deviates from the nominal time by more than  $\pm 20\%$ , the plasma concentration will be flagged and excluded from the summary statistics.

For plasma concentration data the following rules will apply:

- Values that are BLQ will be set to 0 for the calculation of summary statistics.
- Arithmetic mean or median values that are BLQ will be presented as 0.

For PK parameters the following rule will apply:

- Geometric mean and coefficient of variation will not be calculated for  $t_{last}$  or  $t_{max}$ .

#### **8.5.3. Pharmacokinetic Statistical Methodology**

All PK concentrations and parameters will be listed.

Summary tables, mean (+ standard deviation [SD]) figures, overlaying individual figures, and individual figures by treatment and time postdose will be provided for plasma PK concentrations. All figures will be produced on both linear and semi-logarithmic scales.

Summary tables by treatment will be provided for all PK parameters, with the exception of regression-related PK parameters.

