1.5. Study Rationale

AMG 133 has not been previously studied in healthy Japanese or healthy Caucasian subjects without obesity. The objective of this study is to evaluate the PK, safety, and tolerability of a

single SC dose of AMG 133 at 3 dose levels (make mg) in Japanese subjects and at 2 dose levels (mg) in Caucasian subjects. This study will inform about any possible ethnic differences in PK between Japanese and Caucasian subjects.

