3.3. Selection of Doses in the Study

The selection of the doses being evaluated in this study is based on the preliminary PK, safety, and tolerability data from an ongoing FIH study (20180048) evaluating AMG 133 in adult subjects with obesity at single doses ranging from 21 to 840 mg, and multiple-ascending doses following mg administered every 4 weeks (total of 3 doses). In general, AMG 133 has been shown to be safe and well tolerated across the studied dose ranges (21 to 840 mg). The

preliminary PK data from this study demonstrate that intact AMG 133 and total AMG 133 plasma exposures increase in a dose-proportional manner.

, and mg are selected for evaluation in Japanese subjects and will enable The doses an assessment of pharmacokinetic linearity within the AMG 133 dose range that is anticipated to be clinically relevant. The highest dose of mg is selected as this is the highest dose planned for the ongoing multiple-ascending-dose study mg administered every 4 weeks) and is the highest anticipated dose to be tested in a Phase $\frac{1}{2}$ study.

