5.4. Randomization

This is a randomized, parallel-arm study. Japanese subjects will be randomized (1:1:1) to 1 of the 3 treatment groups, and Caucasian subjects will be randomized (1:1) to 1 of the 2 treatment groups. Randomization scheme will be provided by a biostatistician.

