8.3. Pharmacokinetic Analyses

Plasma AMG 133 concentrations will be determined using a validated assay. Individual plasma concentration-time plots for AMG 133 will be presented for each subject as well as mean concentration-time plots for each dose group. Pharmacokinetics parameters of AMG 133 will be calculated using standard noncompartmental methods.

The primary PK parameters will include C_{max} , AUC_{last} , and AUC_{inf} for AMG 133. All other PK parameters will be regarded as secondary and will not be subject to inferential statistical analysis.

Additional parameters may be calculated. Specific details will be presented in the Statistical Analysis Plan for this study.

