## 1. INTRODUCTION

This SAP has been developed after review of the clinical study protocol (Amendment 1 dated 24 August 2021) and electronic case report form (eCRF).

This SAP describes the planned analysis of the pharmacokinetic (PK), safety, and tolerability data from this study. A detailed description of the planned TFLs to be presented in the clinical study report (CSR) is provided in the accompanying TFL shells document.

In general, the analyses are based on information from the protocol, unless they have been modified by agreement with Amgen Inc. A limited amount of information about this study (eg, objectives, study design) is given to help the reader's interpretation.

This SAP must be finalized prior to the lock of the clinical database. Additionally, the SAP and TFL shells should be finalized prior to any programming activities commencing.

This SAP supersedes any statistical considerations identified in the protocol; where considerations are substantially different, they will be so identified. If additional analyses are required to supplement the planned analyses described in this SAP, they may be performed and will be identified accordingly in the CSR. Any substantial deviations from this SAP will be agreed with Amgen Inc. and identified in the CSR.

This SAP is written with consideration of the recommendations outlined in the International Conference on Harmonisation (ICH) E3 guideline *Structure and Content of Clinical Study Reports*, ICH E8 guideline *General Considerations for Clinical Trials*, ICH E9 guideline *Statistical Principles for Clinical Trials*.

The document history is presented in [Appendix 1](#).

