## 2. STUDY OBJECTIVES

The primary objective of the study is:

- to evaluate the PK of AMG 133 after single subcutaneous (SC) administration in healthy Japanese and Caucasian subjects.

The secondary objectives of the study are:

- to evaluate the safety and tolerability of AMG 133 after single SC administration in healthy Japanese and Caucasian subjects.
- to evaluate the incidence of anti-AMG 133 antibodies in healthy Japanese and Caucasian subjects.

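### The SAP text sets no Japanese/Caucasian ratio, dose-proportionality slope or interval for the primary PK parameters, although the protocol puts the study to both uses

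*SAP*

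**What the plan says.** SAP 8.5.3 is the whole of the PK statistical methodology. It lists all concentrations and parameters, and tabulates and plots plasma concentrations. For the parameters it adds: "Summary tables by treatment will be provided for all PK parameters, with the exception of regression-related PK parameters". SAP 8.5.2 implies that these tables include geometric means and coefficients of variation, except for tmax and tlast. No ratio, slope or confidence interval appears in either document.

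The protocol gives the study two comparative uses. Section 1.5: "This study will inform about any possible ethnic differences in PK between Japanese and Caucasian subjects". Section 3.3 says that the three Japanese doses will allow "an assessment of pharmacokinetic linearity within the AMG 133 dose range". Section 8.3 names Cmax, AUClast and AUCinf as primary and continues: "All other PK parameters will be regarded as secondary and will not be subject to inferential statistical analysis".

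The listed primary objective is broader and not comparative: "to evaluate the PK of AMG 133 after single subcutaneous (SC) administration in healthy Japanese and Caucasian subjects". Both documents also say that no hypotheses are tested and that the sample size is practical.

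**The concern.** The design has three Japanese and two Caucasian dose groups, which suits a comparison of populations and a look at dose proportionality. The SAP text stops at one summary per group, so it names no estimate for either question and no measure of how uncertain that estimate would be.

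A reader of the tables can divide two geometric means, but so far as the SAP text goes, nothing fixes in advance which groups are compared, whether doses are pooled, or which error term is used. With seven subjects per group, a bare ratio of two geometric means hides considerable imprecision and can be read as an ethnic difference, or as the absence of one.

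The intention is also unclear. Protocol 8.3 limits its exclusion from inference to the non-primary parameters. The SAP's statement that nothing inferential is planned sits in the safety section (8.6.7), with no counterpart for PK. SAP 8.5.1.2 lets AUCinf be left out of a statistical analysis that no section defines beyond summaries.

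**Working it through.** **Plan's own figure.** 5 groups × 7 = 35, and 3 × 7 + 2 × 7 = 21 + 14 = 35, which agrees with SAP 4 and 5. There is no power or precision figure to reproduce.

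**Inputs**
- n = 7 per group, five groups, 21 Japanese subjects (SAP 4 and 5).
- Between-subject CV: not in the documents. Assumed 30%, range 20% to 50%.
- Doses: redacted. Doses shared between the populations, and the dose spacing, are assumptions.
- Interval level: 90%, chosen here for estimation.

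**Log-scale SD.** s = sqrt(ln(1 + CV²)) = 0.198, 0.294 and 0.472 at CV 20%, 30% and 50%.

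**Geometric mean ratio at one dose, five-group ANOVA error (df = 35 − 5 = 30).** Half-width on the log scale = t(0.95, 30) × s × sqrt(2/7) = 0.180, 0.266, 0.429. Exponentiated, the multiplier on the observed ratio is:
- CV 20%: 0.84 to 1.20
- CV 30%: 0.77 to 1.31
- CV 50%: 0.65 to 1.54

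**Pooled over two shared doses (14 v 14, df 30).** Half-width = t(0.95, 30) × s × sqrt(1/7) = 0.127, 0.188, 0.303. Multiplier:
- CV 20%: 0.88 to 1.14
- CV 30%: 0.83 to 1.21
- CV 50%: 0.74 to 1.35

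This needs two shared doses and assumes the same ratio at both.

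**Effect of the error term.** One pair of groups analysed alone (df = 14 − 2 = 12) gives 0.76 to 1.32 at CV 30%, against 0.77 to 1.31 with the five-group error. The error term hardly matters; pooling does.

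**Power-model slope, three Japanese groups (df = 21 − 2 = 19).** Half-width = t(0.95, 19) × s / sqrt(Sxx), where Sxx is the sum of squares of log dose. For 1:2:4, Sxx = 14 × (ln 2)² = 6.73, and the half-width is 0.13, 0.20 and 0.31 at CV 20%, 30% and 50%.

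At CV 30%, over six assumed spacings:

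| Spacing | Half-width |
|---|---|
| 1:2:3 | 0.244 |
| 1:2:4 | 0.196 |
| 1:3:6 | 0.150 |
| 1:2:6 | 0.150 |
| 1:4:8 | 0.128 |
| 1:3:9 | 0.123 |

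For 1:2:4, the half-width corresponds to a factor of 4^(±0.196) = 0.76 to 1.31 on the exposure ratio from lowest to highest dose.

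These figures show what the added estimates would look like. They do not measure harm done by the present plan.

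**The case against.** The strongest reply is that this is a choice of analysis. The objective is to evaluate PK in both populations, with no comparative objective, margin or decision rule. The two protocol sentences are a rationale and a remark on dose selection, and neither promises a model or an interval. Five by-treatment summaries do inform on both questions, and SAP 8.1 already warns that the sample size is not based on power. All of this stands. A descriptive plan is legitimate, and the 90% level, the ANOVA and the power model are proposals made here.

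The SAP also says that a detailed description of the planned outputs "is provided in the accompanying TFL shells document", to be final before programming starts. That document was not available and may hold more, so nothing here says what will finally be presented. The SAP further allows extra work: "If additional analyses are required to supplement the planned analyses described in this SAP, they may be performed". Such analyses would be supplementary, not planned.

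The statement that no hypotheses are tested does not block the proposal, because a ratio or slope with an interval is estimation.

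A reader might infer that an inferential PK analysis was planned and then dropped. Protocol 8.3 only implies inference for the primary parameters, and SAP 10 declares no significant change from the protocol. SAP references 4 to 7 (log transformation, mixed models, bioequivalence, two one-sided tests) are uncited in the supplied text, but that may be template residue and is an editorial matter. The documents do not support the inference.

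**Conclusion.** The point holds, limited to the SAP text. For Cmax, AUClast and AUCinf that text plans listings and by-treatment tables, and it specifies no estimate or interval for two uses that the protocol names. It should be fixed, because the data will already be collected and the remedy is cheap. It does not make the plan invalid.

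Confidence is high that the SAP text omits these estimates. The sizes are illustrative: they rest on an assumed CV, and the pooled and slope figures also rest on assumed shared doses and spacing.

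A reader might take the proposed ratio as the effect of ethnicity. Protocol 5.4 randomises to dose within each population, so ethnicity is not randomised. The ratio would describe these two samples and could reflect differences in body weight, sex or age.

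**What to change.** Add to SAP 8.5.3, as estimation without hypothesis tests:

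1. An ANOVA with treatment group as a factor on log Cmax, log AUClast and log AUCinf. Report the Japanese/Caucasian geometric mean ratio with a 90% interval at each dose given to both populations. Add a pooled ratio over those doses, stated to assume a common ratio. If no dose is shared, state the comparison used instead.
2. A power-model slope with a 90% interval for each primary parameter in the three Japanese groups.

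State that ethnicity is not randomised and that the ratio may reflect body weight, sex or age, which SAP 8.3 already summarises by group. Align the statistical-analysis wording in 8.5.1.2 with the added analysis. As an editorial step, cite or remove references 4 to 7.

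The cost is SAP wording, two small models and a table per primary parameter. No new data and no protocol amendment are needed. The drawback is wide intervals, which the report should present as the precision that seven subjects per group can give.

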## **8.6. Safety and Tolerability Assessments**

### **8.6.1. Adverse Events**

All AEs will be coded using the Medical Dictionary for Regulatory Activities (MedDRA) Version 24.0 (or higher if a new version is issued during the study; see the DMP for more details).

A treatment-emergent adverse event (TEAE) will be defined as an AE that starts during or after dosing, or starts prior to dosing and increases in severity after dosing.

A treatment-related TEAE will be defined as a TEAE with a relationship related to the study treatment, as determined by the investigator.

All AEs will be listed. In addition to the data recorded in the database, the listings will include derived onset time and duration. Onset time will be calculated from the time of dosing for TEAEs only.

The frequency of subjects with TEAEs and the number of TEAEs will be summarized for the following categories:

- TEAEs (overall, serious, leading to discontinuation, and leading to death) by treatment
- TEAEs by severity and treatment
- Treatment-related TEAEs (overall, serious, leading to discontinuation, and leading to death) by treatment
- Treatment-related TEAEs by severity and treatment

The frequency of subjects will be summarized separately for TEAEs and treatment-related TEAEs by the following:

- System organ class, preferred term, and treatment
- Preferred term and treatment

For the AE data the following rules will apply:

- For the derivation of treatment-emergent status (applicable to all AEs): If the start date/time of an AE is incomplete or missing, an AE will be assumed to not be a TEAE, unless the incomplete start date/time or the end date/time indicates an AE started after dosing.
- For the derivation of treatment-related status (applicable to TEAEs only): If the study treatment relationship for a TEAE is missing, a TEAE will be assumed to not be a treatment-related TEAE.
- For the derivation of onset time (applicable to TEAEs only): If the start date/time of a TEAE is missing, onset time will not be calculated. If the start date/time of a TEAE is incomplete, where possible, the minimum possible onset time will be calculated and presented in ‘ $\geq$ DD:HH:MM’ format (eg, if the date/time of dosing is 01MAY2019/08:00 and recorded start date/time of a TEAE is 03MAY2019, then the minimum possible onset time will be calculated by assuming a TEAE started at the first hour and minute of 03MAY2019 [03MAY2019/00:00], thus will be presented as onset time  $\geq$ 01:16:00 in the listing). If the start date of a TEAE is the same as the date of dosing but the start time of a TEAE is missing, an onset time will be presented as ‘ $\geq$ 00:00:01’. Any clock changes will be accounted for in the derivation.
- For the derivation of duration (applicable to all AEs): If the end date/time of an AE is missing, duration will not be calculated. If the start or end date/time of an AE is incomplete, where possible, the maximum possible duration will be calculated and presented in ‘ $\leq$ DD:HH:MM’ format (eg, if the start of an AE date/time is 01MAY2019/08:00 and its recorded end date/time is 03MAY2019, then the maximum possible duration will be calculated by assuming an AE ended at the last hour and minute of 03MAY2019 [03MAY2019/23:59], thus will be presented as duration  $\leq$ 02:15:59 in the listing). Any clock changes will be accounted for in the derivation.
- For the calculation of TEAE summary statistics: If the severity of a TEAE is missing, that TEAE will be counted under the ‘missing’ category.
- For the calculation of TEAE summary statistics: If a subject experienced multiple TEAEs with the same preferred term for the same treatment, this will be counted as 1 TEAE for that treatment under the maximum severity recorded.

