Medical or scientific judgment is to be exercised in deciding whether serious adverse event reporting is appropriate in other situations such as important medical events that may not be immediately life-threatening or result in death or

CONFIDENTIAL Protocol Reference: 20200290

hospitalization but may jeopardize the subject or may require medical or surgical intervention to prevent 1 of the other outcomes listed in the above definition. These events are typically to be considered serious.

Examples of such events include invasive or malignant cancers, intensive treatment in an emergency room or at home for allergic bronchospasm, blood dyscrasias or convulsions that do not result in hospitalization, or development of drug dependency or drug abuse.

Recording Adverse Events and Serious Adverse Events

Adverse Event and Serious Adverse Event Recording

- When an adverse event or serious adverse event occurs, it is the responsibility of the Investigator to review all documentation (eg, hospital progress notes, laboratory, and diagnostics reports) related to the event.
- The Investigator will then record all relevant adverse event/serious adverse event information in the Event electronic Case Report Form (eCRF).
- The Investigator must assign the following adverse event attributes:
 - o Adverse event diagnosis or syndrome(s), if known (if not known, signs or symptoms);
 - Dates of onset and resolution (if resolved);
 - Did the event start prior to first dose of investigational product, other protocolrequired therapies;
 - Assessment of seriousness;
 - Severity (or toxicity defined below);
 - Assessment of relatedness to the investigational product(s) and/or studymandated procedures;
 - Action taken; and
 - Outcome of event.
- If the severity of an adverse event changes from the date of onset to the date of resolution, record as a single event with the worst severity on the appropriate eCRF.
- It is not acceptable for the Investigator to send photocopies of the subject's medical records to Sponsor in lieu of completion of the appropriate eCRF page.
- If specifically requested, the Investigator may need to provide additional follow-up information, such as discharge summaries, medical records, or extracts from the medical records. In this case, all subject identifiers, with the exception of the subject number, will be blinded on the copies of the medical records before submission to the Sponsor.

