e Adverse events will be recorded from initiation of study treatment on Day 1 until EOS completion. Serious adverse events will be recorded from the time the subject signs the Informed Consent Form until 30 days postdose or EOS visit, whichever is later.

Protocol Reference: 20200290

Labcorp Drug Development Study: 8473020

^fPrior and concomitant medication administration will be recorded beginning at informed consent. In addition, all Investigator-approved medications taken by a subject within 30 days or 5 half-lives (whichever is longer) before Check-in for over-the-counter or prescription medications, and 30 days prior to enrollment for herbal medicines (eg, St. John's wort), vitamins, and supplements, will be recorded on the subject's electronic Case Report Form.

- g Performed in serum at Screening and in urine at all other times for all females. A positive urine pregnancy test will be confirmed with a serum pregnancy test.
- ^h Performed in postmenopausal females only.
- ¹ Electrocardiograms will be collected after the subject has rested in a supine position for at least 5 minutes, and will be obtained prior to the scheduled blood draws.
- ^j Supine blood pressure, supine heart rate, respiratory rate, and oral body temperature will be measured after the subject has been resting in the supine position for at least 5 minutes.
- ^k Clinical chemistry fasted at least 8 hours.
- ¹ eGFR will be calculated using the Modified Renal Disease equation.
- m A full physical examination at Screening and Check-in and a symptom-directed physical examination at other timepoints.
- ⁿ The PK sample collected from predose through 48 hours postdose will have a sampling window of ± 30 minutes, samples collected at outpatient visits will have a sampling window of ± 48 hours. Times of all PK samples will be recorded to the nearest minute.
- Obse administration of AMG 133 is to occur during the morning of Day 1 after an overnight fast of at least 10 hours.

Summary of Amended Protocol Changes

A Phase I, Open-label, Randomized, Parallel-arm, Single-dose Study to Evaluate the Safety, Tolerability, and Pharmacokinetics of AMG 133 Administered Subcutaneously in Healthy Japanese and Caucasian Subjects

Protocol Status: Final Original Protocol Date: 09 August 2021 Protocol Date: 24 August 2021

Investigational Drug: AMG 133

Amgen Protocol Reference Number: 20200290 Labcorp Drug Development Study: 8473020

Study Site:

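### SAP 8.6.1 can leave adverse events with an unresolved start out of every summary table, and its TEAE event count is really a count of subject-by-term pairs

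*SAP*

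**What the plan says.** SAP 8.6.1 sets the default for emergence: "If the start date/time of an AE is incomplete or missing, an AE will be assumed to not be a TEAE". To this it attaches a single exception, worded as follows: "unless the incomplete start date/time or the end date/time indicates an AE started after dosing". All AEs are listed, but every AE summary table in that section is of TEAEs or treatment-related TEAEs.

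The same section then gives display rules that presuppose TEAEs with an unclear start. One reads "If the start date/time of a TEAE is missing, onset time will not be calculated". Another begins "If the start date of a TEAE is the same as the date of dosing but the start time of a TEAE is missing" and shows onset as at least 00:00:01.

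Protocol Appendix 1 requires the investigator to answer, for each event, "Did the event start prior to first dose of investigational product". The SAP rule does not refer to this item. Footnote e of the schedule in Protocol Appendix 8 says "Adverse events will be recorded from initiation of study treatment on Day 1 until EOS completion", and dosing "is to occur during the morning of Day 1".

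On counting, SAP 8.6.1 promises both the number of subjects with TEAEs and the number of TEAEs for the overview and severity tables. It then counts several TEAEs with the same preferred term in one subject as one, at the highest severity recorded.

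**The concern.** Safety and tolerability is a secondary objective, in a population that Protocol 1.5 says has not been studied before. A default of not treatment-emergent removes an event from all tables when its start cannot be placed. The exception meant to limit this can be read in more than one way, so two programmers could classify the same event differently. The record also holds an item that would often decide the matter, and the rule leaves it unused.

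The counting rule is a separate matter and acts even when all dates are complete. A column described as the number of TEAEs would not hold the number of events. Recurrent nausea or vomiting would be undercounted, and milder repeats would vanish from the severity table.

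**Working it through.** **Inputs.** The emergence rule, its exception, the tables and the counting rule come from SAP 8.6.1. Group size comes from SAP 4 (5 groups of 7; 5 × 7 = 35). The pre-dose item is in Protocol Appendix 1, and the recording window and morning dosing are in the footnotes to Protocol Appendix 8. The documents give no rate of incomplete starts. The eCRF and TFL shells were not available.

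**The SAP's own date examples.** Onset: 03MAY2019/00:00 − 01MAY2019/08:00 = 01:16:00. Duration: 03MAY2019/23:59 − 01MAY2019/08:00 = 02:15:59. Both agree with the SAP. They treat a partial date as an interval, so the emergence rule can be tested in the same way.

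**Emergence.** Let the start lie between L and U, with dosing at D. Post-dose onset is shown if L ≥ D, and pre-dose onset if U < D. An end at E adds only that the start is no later than E: U becomes min(U, E) and L does not move. An end before dosing therefore shows pre-dose onset, but no end date can show post-dose onset.

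Take D = 01MAY2019/08:00. A start of 03MAY without a time has L ≥ D and stays in. A missing start with an end of 30APR has U < D and is rightly out. Three kinds of start remain unresolved. Reading A holds that an end date cannot decide; reading B holds that any post-dose end counts. The last column is the rule proposed under the fix, with the investigator's item blank.

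| Start | End | A | B | Proposed |
|---|---|---|---|---|
| missing | none | out | out | in |
| missing | 05MAY | out | in | in |
| 01MAY, no time | none | out | out | in |
| 01MAY, no time | 05MAY | out | in | in |
| MAY only | none | out | out | in |
| MAY only | 05MAY | out | in | in |

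Reading A admits 0 of 6. Reading B admits 3 of 6, exactly those with an end date. If a dosing-day date is itself accepted as pointing to post-dose onset, A admits 0 + 2 = 2 and B admits 3 + 1 = 4. The losses that remain are missing and month-only starts: four under A, and two under B, both without an end date.

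Each of the six patterns could hide either onset. On dates alone, A is wrong for 6 true post-dose onsets, the proposed rule for 6 true pre-dose onsets, and B for 3 of each. The proposed rule reads no more from the dates; it reverses the direction of the error. The improvement comes from using the investigator's item. These are patterns, not frequencies, and they score onset only, not later worsening.

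**Size of one loss.** 1/7 = 14.3 percentage points of a group's incidence.

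**Event count.** With k records of one term in one subject, the SAP counts 1, so the share not counted is 1 − 1/k: 0% for k = 1, 50% for k = 2, 67% for k = 3. Assumed example: 3 subjects, each with 2 mild and 1 moderate vomiting records and 1 mild nausea record.
- Records: 3 × 4 = 12, of which 9 are mild and 3 moderate (3/12 = 25% moderate).
- SAP count: 3 × 2 = 6, of which 3 are mild and 3 moderate (3/6 = 50% moderate).

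**The case against.** The strongest reply concerns Day 1. The SAP gives an onset display for a TEAE dated on the dosing day without a time, and footnote e starts AE recording at treatment. A dosing-day date may therefore itself point to post-dose onset. That is probably the intent, but the emergence rule does not say so. Protocol 7.3.1 has non-serious AEs recorded from enrollment, which comes before dosing, so the footnote does not settle it.

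Incomplete starts should also be few. The SAP was written after review of the eCRF and speaks of start date and time throughout. Subjects stay in the unit until Day 8 and are asked about their condition at least daily. This stands, and it limits the reach of the point.

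The counting rule is stated openly, every repeat appears in the listings, and the unseen TFL shells might carry a footnote. That too is fair, but the SAP's description of the column is still inaccurate.

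Four stronger readings are not supported:

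- A reader might infer that every partial date is lost. A date or month clearly after dosing is kept.
- A reader might infer that the display sentences for TEAEs with unclear starts have no cases under reading A. The TEAE definition also admits pre-dose events that worsen, so some cases could exist. This is not a dependable rescue, because Protocol Appendix 1 records a changing event once, at its worst severity.
- A reader might infer that acute hypersensitivity on Day 1 is expected and would drop out. Protocol 1.6.1.2.2 says only that such reactions may occur, and dosing-day events are probably meant to be kept.
- A reader might infer an undeclared departure from Protocol 8.5, which tabulates any AE. Protocol Appendix 1 leaves the TEAE definition to the SAP, and SAP 1 says that it supersedes the protocol's statistical considerations.

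**Conclusion.** The point holds in a limited form and is minor. Wholly missing and dosing-month-only starts can leave all AE summary tables and remain only in listings. Dosing-day starts without a time are ambiguous rather than clearly lost. The end-date exception is either empty or favours events that have ended, and the rule ignores a required item.

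The effect is zero if all starts are complete. Otherwise it depends on a rate that the documents do not give and that is probably low; one lost subject moves a group's incidence by 14.3 points.

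The counting point does not depend on missing data, but it has an effect only where a subject has repeats of a term. The 25% to 50% shift belongs to the assumed example and is not a forecast. Subject incidences, and the system organ class and preferred-term tables, which count subjects only, are unaffected by it. No inferential safety analysis is planned.

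**What to change.** Amend SAP 8.6.1 in two places.

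1. Replace the emergence default with: *An AE whose start is missing or incomplete and could fall on either side of dosing is a TEAE unless the partial start, an end before dosing, or a yes to the investigator's pre-dose item (Protocol Appendix 1) shows pre-dose onset. An AE with pre-dose onset is a TEAE only if its severity is recorded as increasing after dosing.* State also that a dosing-day start without a time is a TEAE unless that item says otherwise, and that a post-dose end alone does not decide.

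2. Apply the preferred-term collapse to subject counts only and count all records for the number of TEAEs. Alternatively, keep the collapse and relabel the column as subject-by-term pairs.

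The cost is a few sentences, one derivation from an item already required and, if relabelled, a column heading in the TFL shells. No new data are needed. The downside is that where the item is blank, an occasional pre-dose event may be counted as a TEAE.
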